## 8.2 Analysis Populations

The Full Analysis Set (FAS) will include all patients who are randomized to a treatment group and receive at least 1 tablet of IMP or placebo and have at least 1 post-Baseline value for the primary endpoint. This analysis set will be the primary set used for all efficacy analyses, along with the summary of disposition, demographics, and Baseline characteristics. Patients will be analyzed according to the treatment group they were randomized to regardless of the actual treatment received.

The Safety Analysis Set will include all randomized patients who receive at least 1 tablet of IMP or placebo. Patients will be analyzed according to the treatment they actually received. This analysis set will be used for summaries of safety data.

For supplementary analysis purposes, primary and secondary efficacy analyses will be repeated utilizing a Per Protocol Set (PPS), including all patients who do not have any

major protocol deviations that would potentially affect the efficacy of the study drug. Major protocol deviations and any other reasons for exclusion from the PPS will be defined in the SAP and this analysis set will be finalized in a blinded manner prior to database lock. The PPS will be analyzed as actually treated.

The PK Analysis Set will include all patients who receive at least 1 dose of setanaxib and have at least 1 measured concentration at a scheduled PK time point postdose. Patients may be excluded if they have an important AEs or protocol deviations that may impact PK.

#### 8.3 Sample Size

The primary efficacy endpoint is the change in ALP (%) over 24 weeks.

It is planned to enroll approximately 60 to 70 patients. Patients will be randomized and allocated to placebo, setanaxib 1200 mg/day, or setanaxib 1600 mg/day according to a 1:1:1 randomization ratio.

This study is designed to detect a >25% reduction in ALP in setanaxib-treated patients versus a 2.5% reduction in the placebo arm with an overall 2-sided p<0.05. Standard deviations are assumed to be 19% and 24%, respectively, based on the Phase 2a study with setanaxib and the Phase 3 POISE study with Ocaliva. With approximately 16 evaluable patients per arm (48 patients overall) and using a Hochberg step-up test to control alpha across 2 dose comparisons versus placebo, this study has 88.2% global power to detect at least 1 treatment arm as significantly different from placebo and 68.3% power to detect both treatment arms as statistically significant. Also, for the secondary endpoint of change in fatigue, there will be >80% power to detect a 20% reduction in fatigue versus a 2.5% increase in the placebo arm.

An assumed dropout rate of approximately 25% leads to a target sample size of 66 enrolled patients (22 per arm). A range of approximately 60 to 70 enrolled patients allows for variability in the assumed dropout rate.

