#### Study duration:

The study is expected to be conducted from Q3 2021 to Q2 2024. The start of the study will be the date on which the first patient provides informed consent, and the end of the study will be the last patient's last assessment.

The total study duration for an individual patient is up to approximately 32 weeks (approximately 8 months): A 4-week Screening Period, a 24-week Double-blind Treatment Period, and a 4-week Follow-up Period.

**Planned number of patients:** It is planned to enroll approximately 60 to 70 patients. Patients will be randomized and allocated to placebo, setanaxib 1200 mg/day, or setanaxib 1600 mg/day according to a 1:1:1 randomization ratio.

This study is designed to detect a >25% reduction in ALP in setanaxib-treated patients versus a 2.5% reduction in the placebo arm with an overall 2-sided p<0.05. Standard deviations are assumed to be 19% and 24%, respectively, based on the Phase 2a study with setanaxib and the Phase 3 POISE study with Ocaliva. With approximately 16 evaluable patients per arm (48 patients overall) and using a Hochberg step-up test to control alpha across 2 dose comparisons versus placebo, this study has 88.2% global power to detect at least 1 treatment arm as significantly different from placebo and 68.3% power to detect both treatment arms as statistically significant. Also, for the secondary endpoint of change in fatigue, there will be >80% power to detect a 20% reduction in fatigue versus a 2.5% increase in the placebo arm.

An assumed dropout rate of approximately 25% leads to a target sample size of 66 enrolled patients (22 per arm). A range of approximately 60 to 70 enrolled patients allows for variability in the assumed dropout rate.

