Calliditas has therefore decided to amend the protocol changing the study from the current Phase 2b/3 study to a 24-week Phase 2b study of 60 to 70 patients to enable an earlier assessment of the safety and efficacy of setanaxib with the two doses (1600 mg and 1200 mg) versus placebo. With this amended design there is no longer a need for an interim analysis for the assessment of futility and dose selection for a Phase 3 portion, as this is removed. Consequently, the 52-week Extension Phase Treatment Period has been removed.

Given the revision to a Phase 2b study, it is of scientific relevance to focus on an individual endpoint only. Therefore, rather than the originally planned composite endpoint consisting of change in ALP and total bilirubin, the primary endpoint has been amended to evaluate the individual endpoint of change in ALP. The secondary endpoints of change in fatigue and liver stiffness are retained, as is the composite endpoint of changes in markers of cholestasis.

The reduced duration of study treatment from 52 weeks to 24 weeks in combination with the change from a composite primary endpoint to an individual primary endpoint (change in ALP) with fatigue as a secondary endpoint is supported by the preliminary evidence obtained in the Phase 2 study in patients with PBC (GSN000300) as detailed in Section 1.1.4. This study showed statistically significant and clinically meaningful changes in the above mentioned endpoints after 24 weeks of treatment. This is in line with a retrospective investigation, which concluded that measuring ALP at 6 months is of clinical relevance (Murillo Perez et al 2023).

As consequence of the change in primary endpoint, the assumptions for the sample size have been revisited: with approximately 16 evaluable patients per arm (48 patients overall), there will be >80% power to detect a >25% reduction in ALP in setanaxib-treated patients versus a 2.5% reduction in the placebo arm with a 2-sided p<0.05. For the secondary endpoint of change in fatigue, there will be >80% power to detect a 20% reduction in fatigue versus a 2.5% increase in the placebo arm. A dropout rate of approximately 25% leads to a target sample size of 66 patients (22 per arm). A range of approximately 60 to 70 patients allows for variability in the assumed dropout rate.

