10.1.2 Baseline Values for Patient Reported Outcome Assessments

For the Patient Reported Outcome (PRO) assessments PROMIS-short form-Fatigue 7b Daily, PGIS Fatigue and Pruritus and WI-NRS introduced in protocol version 2.0, subjects enrolled under protocol version 1.0 will not have a baseline value collected. The baseline value for subjects enrolled under version 1.0 for these questionnaires will be imputed prior to analysis (Section 12.5.3). For the PBC-40, only the recall period was changed and the baseline value captured under protocol version 1.0 is considered relevant.

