10.11 PROMIS-Short Form-Fatigue 7b Daily

The PROMIS-short form-Fatigue 7b Daily comprises of 7 questions asking the subject to evaluate their fatigue since waking up. Each of the questions on a 5-point scale (range 1-5) with a range of possible values for the score for the daily form from 7 to 35. Higher scores indicate worse functioning for fatigue. This measure will be completed at home by the subject via daily diary over 7 consecutive days prior to the study visits.

Total daily raw scores will be obtained by summing item scores, which are converted into T-scores standardized (mean=50, SD=10). The standardized T-score is reported as the final daily score for each participant. The daily raw scores will be converted into T-scores using the table in Appendix 3 (HealthMeasures, 2019). All questions must be answered in order to produce a valid score using the scoring tables, if the subject does not answer all 7 questions completely, the total daily raw scores are set to missing.

The T-scores for baseline and post-baseline visits will be calculated by averaging the daily T-scores before the visit date (inclusive). The calculation of this average value will proceed only if 4 or more daily T-scores are available; otherwise, the final score will be treated as missing for the corresponding visit. The baseline T score will be defined as the mean of the daily T scores over the last 7 days prior to first treatment administration. For post-baseline assessments only, if data over 8 days is collected, all 8 days will be included in the calculation of the average value.

Approximately 15 subjects will have no baseline value for the PROMIS-short form-Fatigue 7b Daily as they were enrolled under Protocol Version 1.0 and this questionnaire was not added until Protocol Version 2.0. These missing data will not be imputed for the main analysis.

Sponsor: Calliditas Therapeutics Suisse SA

Protocol No: GSN000350

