10.15 PGIS and PGIC Fatigue and Pruritus

PGIS and PGIC-Fatigue and PGIS and PGIC-Pruritus will be recorded prior to each study visit on the day prior to this visit. The PGIS is a global index where subjects will be asked to rate the severity of Fatigue and Pruritus on a 5-point scale within the past 7 days, with choices of 1=none, 2=Mild, 3=Moderate, 4=Severe and 5=Very Severe. Higher scores indicate a worst assessment for fatigue and pruritus.

The PGIC is a 7-point scale reflecting a subject's rating of overall change. Subjects will be asked to rate their overall change with fatigue and pruritus with 1=Very much improved, 2=Much improved, 3=Minimally improved, 4=No change, 5=Worse, 6=Much worse, 7=Very much worse. Higher scores indicate greater severity of fatigue and pruritus, respectively. There is no baseline assessment for PGIC.

No missing data will be imputed

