12.5 Efficacy Analyses

12.5.1 Hypothesis Testing Strategy and Multiplicity

The objective of the primary efficacy analysis will be to evaluate the efficacy of setanaxib versus placebo in the treatment of subjects with PBC and elevated liver stiffness. The aim of the efficacy analysis is to demonstrate superiority of setanaxib over placebo.

The null hypothesis is no difference in change in ALP (%) between setanaxib and placebo over 24 weeks. The alternative hypothesis is that setanaxib demonstrates a difference in change in ALP (%) over placebo.

To control the study-wise error rate, that is, the probability of rejecting the true null hypothesis for the primary endpoint at 1-sided 0.025, a Hochberg step-up procedure will be applied to adjust for 2 dose comparisons versus placebo. The hypothetical example below is used to illustrate the procedure.

• The primary analysis will be performed and the p-values for each setanaxib dose versus placebo will be assigned a rank (#1 for the smallest p-value and #2 for the largest p-value).

Sponsor: Calliditas Therapeutics Suisse SA

Protocol No: GSN000350

• Next, the Benjamini-Hochberg (BH) critical value will be calculated for each p-value, using the formula: (i/m)*Q where *i* = rank of p-value (1 or 2), m is the number of tests (this will be set to 2) and Q is the false positive risk (this will be set to 0.025, for a 1-sided test). Thus, the p-value with Rank 1 will have a BH critical value of 0.0125 and the p-value with Rank 2 will have a BH critical value of 0.025.

Example

Example				
Comparison	Hypothetical observed P-value	Rank	BH-critical value (i/m)*Q	
1. Setanaxib 1600mg vs placebo	0.020	1	0.0125	
2. Setanaxib 1200mg vs placebo	0.024	2	0.025	

• The test with the largest p-value that is less than its Benjamini-Hochberg critical value is comparison #2. This test and all tests with a smaller p-value will be considered significant. Therefore, in this hypothetical example, both dose comparisons will be deemed statistically significant.

For the analysis of secondary and exploratory endpoints, multiplicity will not be adjusted. "Nominal" p-values will be presented and will not be considered as part of the study-wise control of type I error. This is considered appropriate for an exploratory Phase 2b study.

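### The stated power pair (88.2% for at least one dose, 68.3% for both) does not follow from the printed inputs at 16 per arm; the SD assignment, scale and test need stating and the pair restating

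*Protocol*

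**What the plan says.** Protocol 8.3, the Planned number of patients text in the protocol summary, and SAP 8.1 carry the same calculation. The target is a reduction of more than 25% on setanaxib against 2.5% on placebo, with about 16 evaluable patients per arm, 1:1:1 allocation, and a Hochberg step-up over two dose comparisons at overall two-sided 0.05.

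On variability, Protocol 8.3 says the SDs "are assumed to be 19% and 24%, respectively, based on the Phase 2a study with setanaxib and the Phase 3 POISE study" of Ocaliva. The sentence before it names setanaxib first and placebo second, so the natural reading is 19% for setanaxib and 24% for placebo.

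The result is stated as "this study has 88.2% global power to detect at least 1 treatment arm as significantly different from placebo and 68.3% power" for both doses; the summary and SAP 8.1 have the same wording, "68.3% power to detect both treatment arms as statistically significant".

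SAP 12.5.1 fixes the cut-offs: "the p-value with Rank 1 will have a BH critical value of 0.0125 and the p-value with Rank 2" will have 0.025, both one-sided.

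Protocol 1.2 makes a looser claim for the same design: "there will be >80% power to detect a >25% reduction in ALP in setanaxib-treated patients versus a 2.5% reduction in the placebo arm".

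No passage names the test, the scale or the software behind the power figures.

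**The concern.** Both doses share the placebo arm, so the two comparisons are correlated, and the arm SDs fix that correlation. It largely determines how far at-least-one power sits above both-dose power. The stated figures are 19.9 points apart (88.2 − 68.3), which is wide for a placebo arm with the larger SD. That raises the question whether the printed SDs are the ones used.

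What is at stake is traceability. These powers are given to one decimal in three places, yet a reader cannot reproduce them or tell which SD was applied to which arm.

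**Working it through.** **Inputs.** Difference 25 − 2.5 = 22.5 points, the same for both doses (more than 25% taken as 25%); n = 16 per arm; setanaxib SD 19, placebo SD 24 (Protocol 8.3, SAP 8.1). Both doses are declared if the larger one-sided p is below 0.025; otherwise one dose is declared if the smaller p is below 0.0125 (SAP 12.5.1).

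**Parts that reproduce.** Dropout: 16 / 0.75 = 21.3, rounded up to 22 per arm, 66 in total. Single-dose power: the standard error is √((361 + 576)/16) = √58.56 = 7.65, and 22.5 / 7.65 = 2.94. The normal approximation gives Φ(2.94 − 1.96) = 83.7%; the pairwise t test gives 81.1% and Welch 80.8%. The standard error is the same if the SDs change places, so single-dose power for pairwise tests is about 81% under either assignment.

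**Correlation of the two comparisons** = placebo variance / (setanaxib variance + placebo variance). As written it is 576/937 = 0.61; reversed it is 361/937 = 0.39.

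**The pair.** Simulated with at least 400,000 trials per setting (Wilcoxon 200,000; normal by integration). A fresh 400,000-trial run of all rows except Wilcoxon agreed within about 0.2 points.

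| Setting | At least one (%) | Both (%) |
|---|---|---|
| Stated | 88.2 | 68.3 |
| As written, percent scale, n = 16: pairwise t | 85.0 | 71.7 |
| Welch | 84.7 | 71.3 |
| Three-arm error term | 87.8 | 75.6 |
| Normal approximation | 87.9 | 75.0 |
| Wilcoxon | 82.4 | 67.6 |
| As written, log scale, n = 16: pairwise t or Welch | 88.6 to 89.1 | 72.7 to 73.6 |
| Three-arm error term, log scale | 89.0 to 89.4 | 74.0 to 74.7 |
| As written, log scale, n = 15: pairwise t or Welch | 86.3 to 86.8 | 69.1 to 69.9 |
| Common SD 21.6, percent scale, n = 16: Welch | 86.7 | 70.1 |
| Reversed SDs (setanaxib 24, placebo 19), percent scale, n = 16: Welch | 88.2 | 68.7 |
| Reversed SDs: pairwise t | 88.4 | 69.0 |

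**Log-scale conversion (an assumption; the documents give none).** Log SD = √ln(1 + CV²). For setanaxib, CV = 19/75 = 0.253 and log SD = 0.249. For placebo, CV = 24/97.5 = 0.246 and log SD = 0.243. The log difference is ln(0.975/0.75) = ln 1.3 = 0.262 if the reductions are read as geometric means, and 0.264 if read as arithmetic means. The converted SDs are nearly equal, so the correlation falls to 0.49 and the two powers move further apart than on the percent scale.

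**Reading the table.** No method tried at n = 16 with the SDs as written gives both stated figures. For the t-type and normal tests listed, both-dose power is above 68.3 by between 71.3 − 68.3 = 3.0 and 75.6 − 68.3 = 7.3 points. Wilcoxon comes close on both-dose power (67.6) but misses at-least-one power by 88.2 − 82.4 = 5.8 points. At-least-one power falls on either side of 88.2: about 3 points lower with pairwise tests on percent change, and 0.4 to 1.2 points higher on the log scale.

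**Effect size.** On the percent scale, raising the effect until at-least-one power is 88.2% lifts both-dose power to 75.5% to 76.6%. Lowering it until both-dose power is 68.3% drops at-least-one power to 82.5% to 83.3%. A target above 25% therefore does not explain the pair on that scale.

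**The case against.** The strongest objection is scale. The primary analysis models log(ALP) − log(Baseline) in an MMRM (Protocol 8.4.1.1, SAP 12.5.2.1), so a two-sample test on percent change is not the planned analysis. On the log scale with the SDs as written, at-least-one power at 16 per arm is about 89%, so 88.2% is not too high. At 15 per arm, which the word approximately could cover, pairwise log-scale tests come within 2 points of both stated figures. This stands, and it rules out saying that no method can approach the pair or that at-least-one power is plainly overstated. It does not rescue the pair at 16 per arm, where log-scale both-dose power is still 4 to 6 points above 68.3%. The MMRM itself cannot be checked, because no within-patient correlation is given.

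Second, a reader might infer that the two SDs were swapped. The reversed assignment is the closest match found, but the documents do not establish it. A common SD of about 21.6 also comes within 2 points of both figures, and listing the setanaxib study first favours 19% for setanaxib. The word respectively could also attach to the two source studies rather than to the arms. The source calculation is not in the documents.

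Third, a reader might infer that the trial is underpowered. It is not, on these inputs: single-dose power is about 81% with pairwise tests on percent change under either assignment, in line with Protocol 1.2. A difference of a few points changes no decision in an exploratory Phase 2b study. That is a reason to treat the point as minor, not to leave the figures as they are.

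**Conclusion.** The concern holds as a minor error of statement. With 16 per arm and the SDs as the text assigns them, the pair 88.2% and 68.3% is not reproduced. The consistent discrepancy is in both-dose power, stated about 3 to 7 points too low against pairwise t, Welch, three-arm or normal tests on percent change and t-type tests on the log scale. The direction of any error in at-least-one power depends on scale and test.

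This rests on equal effects of 22.5 points for both doses, normal data on the scale analysed, and reading 19% as setanaxib and 24% as placebo; the log-scale figures also rest on the CV conversion. A swap of the SDs is a plausible cause, but it is not shown. The sample size of 22 per arm and the claim of more than 80% power in Protocol 1.2 are unaffected.

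**What to change.** Check the source calculation for which SD was used for which arm, on what scale and with which test. Then do one of the following:

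- If 24% was used for setanaxib and 19% for placebo, and that was intended, correct the SD assignment in the text.
- If 19% (setanaxib) and 24% (placebo) are right, keep them and restate both powers with scale and test named. For pairwise t or Welch on percent change these are about 85% for at least one dose and 71% to 72% for both. If another scale or test is chosen, the figures must be those of that method.

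Make the same change in the protocol summary, Protocol 8.3 and SAP 8.1. The cost is wording in three passages and one rerun of the power calculation, with no change to patients, sample size or analysis model.

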## 8.4 Statistical Methods

## 8.4.1 Analysis of Efficacy

Efficacy data will be presented and analyzed using the FAS and a supplementary analysis will be performed using the PPS.

#### 8.4.1.1 Primary Endpoint Analysis

The primary endpoint is listed in Section 2.1.

For the primary efficacy analysis, each setanaxib treatment group (1600 mg and 1200 mg) will be compared with placebo. The primary estimand is to assess the change in ALP (%) over 24 weeks in patients with PBC, elevated liver stiffness, and intolerance or inadequate response to UDCA.

The following intercurrent events will be considered and further detailed in the SAP. Patients who start additional PBC-related medication(s) after Randomization will have their IMP discontinued (Section 6.7). These patients will be included in the analysis, but efficacy data collected after the start of the new therapy will be excluded. PBC-related medication(s) will be identified through blinded medical review prior to database lock. For all other patients who discontinue from treatment prior to Week 24 but return for the Week 24 Visit (Visit 8), the Week 24 result will be used regardless of the occurrence of the intercurrent event. Patients with missing results will have their values imputed based on observed data. Further details will be defined in the SAP.

The primary endpoint will be evaluated using a mixed model for repeated measures (MMRM) with log(ALP) - log(Baseline) as response with log(Baseline) as a continuous covariate, ALP stratification (<3.0×ULN or ≥3.0×ULN), treatment and visit as categorical covariates and treatment by visit as interaction term. All ALP data captured at Weeks 2, 4, 8, 12, and 24 will be included in the model. The relative mean change from Baseline at Week 24 will be estimated and corresponding 2-sided 95% confidence intervals will be calculated. The relative mean change and confidence intervals will be calculated. The relative mean change and confidence interval will also be converted to the percentage scale, for presentation purposes.

An unstructured covariance matrix will be used to model the within-patient correlation of data. The Kenward-Roger's degrees-of-freedom adjustment will be used. Restricted maximum likelihood will be used to obtain parameter estimates. The least squares means will be estimated by visit along with the associated 95% confidence intervals and p-values with the analysis taken from the estimate at 24 weeks. In the case of insufficient patients at either level of the stratification, the stratification factor will be removed from the model.

Model assumptions of the MMRM will be assessed using residual plots (such as q-q plots, histograms, box plots, and scatter plots). If the model above does not converge, heterogeneous Toeplitz covariance structure will be used instead of the unstructured covariance matrix. If convergence still does not meet, the Toeplitz structure then will be used.

